#### 8. Comparison of Ki-67 expression changes between study subjects and a historical cohort.

Participants will be matched with a historical nonrandomized control group. The control group will provide a reference for how Ki-67 may change based on differences in specimen collection (endometrial biopsies versus surgical specimen) and time between biopsy and surgery, independent of exemestane exposure.

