Participants will place a tampon 8-12 hours before surgery. For US based sites, a tampon kit will be mailed to the participants. The study agent will be mailed along with an additional tampon kit. The kit will include 2 tampons (one to be inserted prior to surgery and one as back up) and instructions to insert the tampon (appendix D).

**For EOG site only**, the participants will come back to the clinic the day before surgery and have the second tampon placed by a study nurse.

Surgery must occur between Days 22-43 of the study. On the day of surgery, participants will undergo a physical exam, laboratory tests (Complete Blood Count (CBC) with differential and platelets, Comprehensive Metabolic Panel (CMP), estradiol and progesterone), and an additional blood draw for plasma levels of exemestane. In addition, adverse events and concomitant medications will be reviewed. At the time of surgery, the self-inserted tampon will be removed by the surgeon.

Following surgery, and after completion of necessary standard of care surgical pathology, an additional section of the tumor (up to 1x1x1 cm) will be collected, cut in half and snap frozen as per institutional policy and stored for genetic analysis. If there is not a visible lesion, a random 1x1x1 cm area from the endometrium will be selected. This can be smaller if the pathology team needs to review more of the endometrium. The amount and location of the sample is at the investigators clinical discretion. In addition, ten unstained 5 $\mu$ m formalin fixed paraffin embedded (FFPE) slides will be obtained from the primary tumor surgical specimen for IHC biomarker analysis.

**For EOG site only**, follow-up at the standard of care post-operative visit will be performed in order to collect long-term safety information of the study treatment, whether or not the participant has any ongoing adverse events at the surgery visit.

If any reported adverse events attributed to the study agent are ongoing on the day of surgery, the participant will be contacted by the study team on or before the post-operative visit to perform safety assessments for ongoing adverse events or symptoms.

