## 7. CLINICAL EVALUATIONS AND PROCEDURES

### 7.1 Schedule of Events

Evaluation/ Procedure	Pre-screening Contact	Baseline (pre-surgical) clinic Visit (Day -30 to Day 0)	Day 1	Day 15 Phone Contact (±2 Days)	1 Day Prior to Surgery Phone Contact (-2 Days)	Final Study Visit Surgery Day 22 - 43	Follow up contact on or before 1st Post-Surgery Follow-up 
Verbal telephone consent (Biopsy consent*)	X						
Informed consent		X					
Mailing tampon and consent form (US only)	X						
Reminder for tampon insertion (US Only)		X 			X		
Assess eligibility	X 	X					
Medical history		X					
Review of concomitant medications		X		X	X	X	X
Baseline symptoms		X					
Adverse events				X	X	X	X
Physical exam with ECOG score		X					X
Demographics		X					
Vitals including height, weight and BMI		X					X 
CBC/Diff/Plt		X					X
Comprehensive Metabolic Panel (CMP) or Equivalent 		X					X
Estradiol and Progesterone 		X					X
Research blood draw 		X					X
Serum FSH level for confirmation of post-menopausal status, if applicable 		X					
Endometrial biopsy 	X*	X					
Tampon insertion by research team*		X*			X*		
Surgical pathologic samples of endometrium							X
Vaginal cell collection via tampon (inserted 8-12 hours before appointment/surgery)		X	X*				X
Mailing study agent / (Dispense study agent*)		X 	X*				
Telephone reminder to start study agent			X 				
Start study agent			X				
Collect study agent							X
Review pill diary/record and assess compliance				X	X	X	
Reminder for last dose					X		
Tobacco and Alcohol Assessments		X 					X 

\* Procedures only applicable to E. O. Ospedali Galliera (EOG) site.

1. Phone call or in person contact is only performed if there are any unresolved AEs (with a possible, probable or definite attribution to the study agent) on the day of surgery. For EOG Site only: AEs for long term effects of study treatment will be assessed at this follow up visit.
2. Reminder phone call for tampon insertion a day prior to baseline (pre-surgical) clinic visit.
3. Assess diagnosis based on available pathology report and age of the participant (US only)
4. Height will not be recorded on the day of surgery. Previously recorded height will be considered for BMI calculation

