### 7.3 Baseline (pre-surgical) clinic Visit

A written informed consent form will be signed before any study related procedures (specifically blood draws and biopsy) are conducted at the baseline (pre-surgical) clinic visit.

The following procedures will be performed to determine eligibility (within 30 days of starting exemestane):

- Review of diagnostic pathology report, medical history, concomitant medications, and baseline symptoms
- Physical exam with vitals including height, weight, and BMI as well as ECOG performance score.
- Endometrial biopsy will be performed to ensure an adequate amount of tissue for IHC and genetic analysis. If a biopsy is not feasible, or if insufficient tissue is obtained (noted by the physician at the time of biopsy), the subject will not be eligible for this trial, as comparative IHC is the primary outcome for the study.
  - This biopsy is done for research purposes only.
  - Endometrial biopsies will be performed in the gynecologic oncology clinic by the gynecologic oncologist. This is a common outpatient procedure, which is performed during the pelvic/speculum exam (part of the standard pre-surgical physical exam). With the speculum in place, the physician will pass an endometrial pipelle through the cervix and then sample endometrial cells through standard biopsy techniques. This procedure is similar to a Pap smear in terms of sample acquisition except instead of scraping cells from the cervix, a straw-sized pipelle is passed through the cervix and cells are aspirated from the endometrium.
  - No additional sedation or monitoring is required for this procedure.
  - Two biopsy “passes” with the endometrial pipelle will be performed. The first specimen will be formalin-fixed, paraffin embedded (FFPE), and sent to the University of Minnesota for IHC analysis and central pathologic review. The second specimen will be placed directly into a stabilizing agent (AllProtect) for genetic analysis.
  - This sample will be destroyed if the participant does not meet eligibility criteria

Note that the subjects will consent to the study prior to their physical examination. It is important to minimize discomfort to the study subjects and therefore we plan to perform the research-related endometrial biopsy at the same time as the standard pre-operative pelvic/speculum exam. This is done to avoid the discomfort of having multiple pelvic exams and to reduce the number of visits for the study participant.

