### **8.2.7 Comparison of Ki-67 expression changes between subjects and a historical cohort**

The reason a historic cohort will be studied is to provide the context in which to assess the effects of exemestane in reducing Ki-67 from baseline to post-exposure to exemestane. Specifically, there may be a change in Ki-67 expression from pretreatment biopsy to final surgical specimen in the historical control cohort suggesting that time alone (between biopsy and surgery) or potentially differences in tissues

acquisition (biopsy versus surgical specimen) may have an impact on Ki-67 expression.

The study participants will be matched with a historical nonrandomized control group based on age (+/- 5 years), disease type and BMI (>20-24, 25-30, > 30). This control group will provide a reference for how Ki-67 may change based on time (specifically time between biopsy and surgery which has to be within 42 days) or differences in specimen collection (endometrial biopsies versus surgical specimen), independent of exemestane exposure.

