### **13.2 Randomization/Stratification**

In the absence of randomized placebo controls, we will obtain age, disease and BMI matched comparator cohort from each institution’s biobank. The historical samples from each matched control will need to be obtained within 42 days of each other in order to be consistent with the study participants. This matching will be one-to-one. A comparison of Ki-67 expression between subjects on this study and historic controls is not a primary goal of the study. The primary outcome is the overall change in Ki-67 expression between pre and post-treatment of each subject. The reason a historic cohort will be studied is to provide the context in which to assess the effects of exemestane in reducing Ki-67 from baseline to post-exposure to

exemestane. Specifically, there may be a change in Ki-67 expression from pretreatment biopsy to final surgical specimen in the historical control cohort suggesting that time alone (between biopsy and surgery) or potentially differences in tissues acquisition (biopsy versus surgical specimen) may have an impact on Ki-67 expression.

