### 13.4 Primary Objective, Endpoint(s), Analysis Plan

The primary objective is to determine if there is a decrease in proliferation index, measured by percent Ki-67 expression, in CAH/EIN or low grade endometrial cancer cells from baseline to post-exposure. Therefore, the primary endpoint is the absolute change in Ki-67 expression in endometrial cancer cells from baseline to post-exposure. We will evaluate the change from baseline to post-exposure in absolute change in Ki-67 using one-sample Student's t-test or Wilcoxon signed-rank test, as appropriate. In addition, we will evaluate the change relative to the change recorded in the historic cohort.

Ki-67 values for patients with endometrial cancer are available in prior research. When the patients from this paper are limited to those with low grade cancers, the mean (standard deviation) of the decrease from baseline was 7.2 (7.5) among the treated patients. Given an SD of 7.5, the table below shows the detectable effect sizes (defined as the mean change divided by the standard deviation of the change) and mean changes for a one-sided test for significance level  $\alpha=0.05$  and various power ( $1-\beta$ ) levels for the primary endpoint given the effective sample size of 30. For example, using an 0.05 level one-sided one-sample Student t-test, we would be able to detect an effect size of 0.50, which corresponds to a mean decrease of 3.8, with 0.85 power.

	Power		
	0.80	0.85	0.90
Effect Size	0.46	0.50	0.55
Mean Decrease	3.5	3.8	4.1

The mean decreases in this table are smaller than the mean difference in the treatment group for those with low grade endometrial cancer in the prior research with letrozole. We are including CAH/EIN in addition to low grade endometrial cancer in the current study and therefore it is not unreasonable to expect a lesser treatment effect for these patients with a less severe form of the disease. For these reasons, we feel there is a need to power for smaller differences.

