It is estimated that 50% of the patients will have CAH/EIN and 50% will have low grade endometrial cancer. For subgroups each with 15 patients, using a 0.05 level one-sided one-sample Student t-test, and assuming the same standard deviation as above, there will be power of 0.8-0.9 to detect a mean decrease ranging from 5.1-6.0. Because of the nature of the study being exploratory, we are not making adjustment for multiplicity of testing in subgroups defined by CAH/EIN vs low grade carcinoma.

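### The 42-day limit for historic controls matches the participants' dosing limit, not their biopsy-to-surgery interval, so the Ki-67 comparison is misaligned on time

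*Combined protocol and SAP*

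**What the plan says.** The primary analysis (sections 8.1 and 13.4) is a one-sample t-test or Wilcoxon signed-rank test of the absolute change in Ki-67 from research biopsy to surgical specimen. The power figures are for that test, including those for the two disease subgroups: "For subgroups each with 15 patients, using a 0.05 level one-sided one-sample Student t-test". The historic cohort then has one sentence in 13.4: "In addition, we will evaluate the change relative to the change recorded in the historic cohort".

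Its purpose is given in section 1.2, item 8: "The control group will provide a reference for how Ki-67 may change based on differences in specimen collection", and also on time between biopsy and surgery, independent of exemestane. Controls are matched one to one on age, disease type and BMI. Section 8.2.7 sets the time rule, "time between biopsy and surgery which has to be within 42 days", and section 13.2 gives the reason: samples are to be "within 42 days of each other in order to be consistent with the study participants". Section 3 repeats the 42-day limit. No lower limit is set. Section 13.2 also says that the comparison is not a primary goal.

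For participants, the Schedule of Events (7.1) heads the visit at which US research biopsies are taken "Baseline (pre-surgical) clinic Visit (Day -30 to Day 0". Section 7.3 puts it this way: "The following procedures will be performed to determine eligibility (within 30 days of starting exemestane". Section 3 fixes the other end: "Surgery must occur between Days 22-43 of the study". Sections 3 and 5.1 use 42 days as the maximum duration of dosing.

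**The concern.** The 42-day rule is justified as consistency with the participants, but it takes its figure from a different quantity. Dosing runs from Day 1 to the day before surgery. The biopsy-to-surgery interval also includes the gap between the research biopsy and Day 1, which may be as long as 30 days. Participants therefore have a floor of 22 days and a ceiling well above 42; controls have no floor and a ceiling of 42.

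Time is one of the two factors that the cohort exists to represent. If Ki-67 drifts between biopsy and surgery without treatment, controls observed over shorter intervals show less of that drift. The remainder stays in the treated-minus-control difference. A downward drift would flatter exemestane and an upward one would hide part of its effect. Section 2.1 says that the data will guide later studies, so a misattributed effect would carry forward.

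**Working it through.** **1. The plan's own figures.** Inputs from 13.4: SD of change 7.5, n = 30, one-sided 0.05. Power = P(T > t(0.95, 29)), where T is noncentral t with 29 degrees of freedom and noncentrality (mean decrease / 7.5) × √30.

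| Mean decrease | Stated power | Recomputed |
|---|---|---|
| 3.5 | 0.80 | 0.803 |
| 3.8 | 0.85 | 0.856 |
| 4.1 | 0.90 | 0.899 |

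For n = 15 the detectable decreases are 5.07 (power 0.80) and 5.96 (power 0.90), against the stated 5.1 to 6.0. All figures reproduce as tests against zero.

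**2. Biopsy-to-surgery intervals, US sites.**
- Shortest: biopsy Day 0, surgery Day 22, so 22 days. The Schema agrees, with baseline at least 22 days before surgery.
- Longest: biopsy Day −30, surgery Day 43, so 30 + 43 = 73 days. By the wording of 7.3 (within 30 days of starting drug, that is, of Day 1) it is 30 + 42 = 72.
- Even with every biopsy on Day 0, the range is 22 to 43 days.
- Controls: 0 to 42 days.

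**3. Italian site.** Sections 3 and 7.2 place the research biopsy at the diagnostic hysteroscopy, before main consent and baseline, so the interval may be longer. Section 7.3, however, lists the biopsy among procedures within 30 days of starting drug with no exception for this site, and exclusion 4.2.12 places it at the baseline visit. The upper limit is not clearly stated.

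**4. Size of the residual drift.** The documents give neither a drift nor actual intervals, so both are assumed. For a linear drift common to both cohorts:

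bias = drift per day × (mean participant interval − mean control interval).

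Intervals are taken as uniform over the ranges shown.

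| Participants (days) | Controls (days) | Gap in means (days) | Bias at 0.5 point per 10 days | Bias at 1.0 point per 10 days |
|---|---|---|---|---|
| 22–73 | 0–42 | 47.5 − 21 = 26.5 | 1.3 | 2.7 |
| 22–43 | 0–42 | 32.5 − 21 = 11.5 | 0.6 | 1.2 |
| 22–43 | 14–42 | 32.5 − 28 = 4.5 | 0.2 | 0.5 |

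**5. Precision of the matched comparison.** Assume a control SD of 7.5 (none is given), 30 pairs and within-pair correlation ρ. SD of the within-pair difference = 7.5 × √(2(1 − ρ)); 95% half-width = 2.045 × SD / √30.
- ρ = 0: SD 10.61, half-width 3.96, two-sided 0.05 power at 3.8 points 0.475.
- ρ = 0.3: SD 8.87, half-width 3.31, power 0.62.

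**The case against.** The strongest reply is that this is a single-arm phase IIA pilot whose historic comparison is openly secondary. The protocol itself says that time and specimen type may move Ki-67. It names the contrast (change relative to change) and matches one to one. All of that stands, and it limits the weight of the point.

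A second reply is that long intervals may be rare. Section 3 does the eligibility tests in one visit so that treatment starts promptly, section 6.8 expects confirmation within two hours at US sites, and a return biopsy one to two weeks after consent shortens the interval. Controls with intervals near zero may also be rare. This stands too: the 26.5-day gap is a scenario, and the true gap could be a few days. It does not rescue the rule, because the plan neither limits participants to 42 days nor gives controls a floor.

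A reader might infer that the primary test is invalid, or its power overstated, because a fall against zero cannot be attributed to the drug. The documents do not support that. The objective in 1.1 and 13.4 is whether Ki-67 decreases, the one-sample test answers it, and the figures reproduce. Attribution is a matter of interpretation, which is why the secondary comparison should be well aligned.

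A reader might also put the Italian interval at up to 87 days (45 + 42). That requires reading the 45-day limit on the pathology report as a limit on the biopsy and taking baseline as Day 1, and it sits badly with 7.3 and 4.2.12.

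**Conclusion.** The 42-day rule does not do what 13.2 says it does. This follows from the visit windows alone: participants at US sites may have 22 to 73 days (72 by 7.3) between biopsy and surgery, and controls 0 to 42. The cohort is therefore misaligned on one of the two factors it is meant to represent.

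The effect on the result cannot be determined from the documents. The biases of 0.6 to 1.2 points (participants at 22 to 43 days) and 1.3 to 2.7 points (22 to 73 days) rest on an assumed linear drift of 0.5 to 1.0 point per 10 days and uniform intervals, with controls over 0 to 42 days. They shrink as the controls' intervals approach the participants'. For scale, the plan's detectable decrease at 0.85 power is 3.8 points.

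The lack of a named estimator or confidence interval for the comparison is missing detail, worth settling in the same amendment but not an error in itself. The change should be made. It concerns a secondary comparison and leaves the primary analysis as it is.

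**What to change.** **Sections 3, 8.2.7 and 13.2.** Replace the fixed 42-day limit: select each control, within the existing matching factors, with a biopsy-to-surgery interval as close as archives allow to her matched participant's actual interval. Report the distribution of intervals in both cohorts, and repeat the comparison in the pairs whose intervals are comparable. State which limit applies to the Italian research biopsy, so that its interval can be described.

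**Section 13.4.** Keep the one-sample test and its power figures, and keep the historic comparison non-primary. State that it will be reported as the mean within-pair difference in Ki-67 change with a 95% CI, with a baseline-Ki-67-adjusted estimate as a sensitivity analysis. Say that any drug effect will be interpreted in light of it.

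**Cost.** Wording and one more matching factor, with no new patients. Section 10.1.1 ships control tissue at the end of the study, so participants' intervals can be known before controls are finalised. The main downside is that some participants may lack a close match. The caseloads in 4.4 over the 5 years allowed in section 3 give (3 × 100 + 10 × 12) × 5 = 2,100 patients, but that counts patients seen, not tissue held. US diagnoses come on referral reports, so biopsy blocks may be elsewhere. The comparison is also imprecise, as step 5 of the working shows: with control SD 7.5 assumed, a half-width of about 4.0 points, or 3.3 at pair correlation 0.3. The plan should state this precision in advance.

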### 13.5 Secondary Objectives, Endpoints, Analysis Plans

The secondary objectives are to examine and test change in circulating serum estradiol and progesterone, histology, and tissue biomarkers. Additionally, we will correlate response with tumor DNA mutations, and

protein and DNA markers via tampon recovery. Therefore, the secondary endpoints are the changes in circulating serum estradiol and progesterone levels, in tissue biomarkers such as apoptosis as measured by cleaved caspase 3 level, proliferation as measured by cyclin D1 level, and insulin pathway as measured by pAKT and IGF-1R levels, and hormone receptor changes as measured by ER, PR and AR.

All tumors will be sequenced via Next Generation Sequencing panel testing and also be tested for microsatellite instability. Results of tumor genetic testing will be correlated with exemestane response as defined by the change in Ki-67 expression.

As an exploratory endpoint, we will attempt to identify the genetic mutation of the primary tumor by performing Next Generation Sequencing of tampon collected DNA. Additionally, vaginal proteomic analysis will also be performed via tampon collection and correlated with tumor response to exemestane as defined by the change in Ki-67 expression.

To evaluate the reliability of methylation measurement assayed on the 850K EPIC chip, an intraclass correlation coefficient (ICC) will be calculated for each CpG site using the technical replicates (using 4 blinded duplicate measurements). We aim to classify the CpG sites into multiple reliability groups, by modeling the distribution of ICC values using a mixture distribution.

The degree of methylation will be determined using Illumina GenomeStudio software. The methylation score for each CpG will be represented as a beta ( $\beta$ ) value calculated by dividing the fluorescence intensity of the methylated allele by the sum of the intensities of the methylated allele and unmethylated allele.  $\beta$ -values may take any value between 0 (non-methylated) and 1 (completely methylated). Background subtraction will be conducted with the GenomeStudio software using built-in negative control bead types on the array. An average normalization will also be applied in GenomeStudio to minimize scanner-to-scanner variation using ~90 normalization probe pairs included on the array, which target housekeeping regions with no underlying CpG sites. These probes will be used to independently calculate normalization values in the green and red channels so that all samples have the same average intensity.

We will identify individual DNA methylation sites ( $\beta$  values as independent variables) in the 850K EPIC chip that are either overexpressed or underexpressed in endometrial tumor DNA by focusing on the tails of distribution of the  $\beta$  values. We will evaluate whether those individual methylation sites can be detected in the matched tampon DNA. We realize that this study is not powered to comprehensively identify all individual DNA methylation markers in endometrial cancer and will perform these analyses to potential targets that can be confirmed in future studies.

Vaginal and tumor DNA methylation studies will be performed; the signals from methylated (M) and unmethylated (U) bead types will be used to calculate  $\beta = M/(U + M)$  for the 850,000CpG sites that the EPIC methylation chip evaluates. Correlations will be tested between vaginal and tumor DNA methylation at each CpG site, adjusting for covariates, possibly including age. Linear mixed models adjusting for covariates such as age and histology (CAH/EIN vs grade 1/2) will be used to test for relationships between vaginal DNA methylation at CpG sites and the primary endpoint, change in Ki-67. A False Discovery Rate (FDR) q-value of 0.05 will be applied to adjust for multiplicity in these tests; where an FDR is not appropriate, a Bonferroni correction will be used.

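### Four duplicates give single-site ICCs too imprecise to assign individual CpG sites to reliability groups, and a mixture fitted to the raw ICCs can produce groups from sampling error alone

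*Combined protocol and SAP*

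**What the plan says.** Section 13.5 of the combined protocol and SAP has a short reliability step for the EPIC methylation chip. Its purpose is given as "To evaluate the reliability of methylation measurement assayed on the 850K EPIC chip". The method is that "an intraclass correlation coefficient (ICC) will be calculated for each CpG site using the technical replicates (using 4 blinded duplicate measurements"). The result is then used as follows: "We aim to classify the CpG sites into multiple reliability groups, by modeling the distribution of ICC values using a mixture distribution". The same section computes methylation values "for the 850,000CpG sites that the EPIC methylation chip evaluates", so about 850,000 ICCs would enter the mixture.

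The section does not give:
- the tissue that supplies the duplicates (tumor or tampon DNA), or whether the 4 counts pairs or single runs;
- the expected precision of an ICC;
- the mixture's component family, a rule for the number of groups, a check against a single group, or any allowance for sampling error;
- any later use of the groups.

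The section does contain a caveat: "We realize that this study is not powered to comprehensively identify all individual DNA methylation markers in endometrial cancer". That sentence concerns finding markers and does not address the precision of the reliability step.

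**The concern.** An ICC compares variance between samples with variance between repeat runs. With four duplicated samples, the first has 3 degrees of freedom and the second 4, so the estimate for one site can land almost anywhere. Two things follow.

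- A site's group label is driven largely by chance.
- The spread of the 850,000 ICCs contains a large sampling-error component. A mixture that ignores this can read the spread as real differences in reliability.

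What is at stake is whether the published classification says anything dependable about a given CpG site. It is an assay-quality statement inside a secondary, exploratory part of a pilot study.

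**Working it through.** The plan states no precision or sample-size figure for this step, so there is none to reproduce.

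**Inputs.** From Section 13.5: 4 duplicates, read as n = 4 samples with 2 runs each, and 850,000 sites. Assumed: the true ICC, shown at 0.5, 0.8 and 0.9; normal errors; and, in the simulations, independent sites.

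**Sampling distribution of one ICC.** For the one-way ICC with duplicates, F = MSB/MSW follows ((1+ICC)/(1-ICC)) × F(n-1, n), and the estimate is (F-1)/(F+1). With n = 4 the reference is F(3,4), whose 2.5% and 97.5% points are 0.0662 and 9.979.

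At a true ICC of 0.8 the multiplier is 1.8/0.2 = 9:
- lower limit: 9 × 0.0662 = 0.596, and (0.596-1)/(0.596+1) = -0.25;
- upper limit: 9 × 9.979 = 89.8, and (89.8-1)/(89.8+1) = 0.98;
- an estimate below 0.5 means F below 1.5/0.5 = 3, so P(F(3,4) < 3/9) = 0.197.

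| True ICC | Central 95% range of estimates | Below 0 | Below 0.5 | Above 0.9 |
|---|---|---|---|---|
| 0.5 | -0.67 to 0.94 | 20% | 52% | 5% |
| 0.8 | -0.25 to 0.98 | 5% | 20% | 24% |
| 0.9 | 0.11 to 0.99 | 2% | 8% | 48% |

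Conversely, a site with an observed ICC of 0.9 has an exact 95% confidence interval of 0.31 to 0.99.

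**Other readings of the 4, at a true ICC of 0.8.** Two samples run twice: -0.98 to 0.99. Four samples run four times each: 0.04 to 0.95. One sample run four times gives no between-sample variance and so no ICC. None of these makes single-site values precise.

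**Best achievable classification.** Suppose sites come half and half from two true ICC levels and are assigned by the optimal rule. With 4 pairs, the misclassified share is 16% for 0.3 against 0.9, 22% for 0.5 against 0.9, 30% for 0.7 against 0.9, and 32% for 0.5 against 0.8. With 20 pairs, the 0.5 against 0.9 figure falls to 2.4%.

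**False groups.** 850,000 sites were simulated with the same true ICC, and normal mixtures of one to four components were fitted, with BIC choosing the number.
- Raw scale: BIC chose four, the largest number tried, at true ICCs of 0.5, 0.8 and 0.9. At 0.8 the spurious group means were 0.08, 0.58, 0.81 and 0.93, with weights 14%, 27%, 33% and 27%.
- Fisher-z scale: BIC chose three or four.
- Beta components (50,000 sites, all at 0.6): BIC was -35919 for one component, -39774 for two and -39941 for three, so three was preferred, with means 0.13, 0.47 and 0.74.
- Components built on the exact F(3,4) sampling distribution: BIC favoured one group, by about 27.

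**The case against.** **False groups are not peculiar to four pairs.** A reader might infer that the small number of duplicates by itself makes spurious groups certain. The documents do not support that, because the plan names no component family and the result depends on it. With beta components and a common ICC of 0.6, BIC still prefers two groups to one at 20 pairs (-121041 against -120508) and at 50 pairs (-167327 against -167127). At four pairs, a mixture carrying the correct sampling error returns one group. Much of the splitting is therefore a misfit of the family, exposed by a very large number of values. This objection stands. What four pairs add is the distance between the false groups (0.08 to 0.93 at a common ICC of 0.8) and the misclassification of single sites, which the correct family does not cure.

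**No filtering is planned.** A reader might also infer that reliable sites would be dropped and unreliable ones kept. Section 13.5 says nothing of the kind. It plans its correlations at each CpG site, with FDR or Bonferroni control and no reliability filter. This stands too, and it limits the consequence to the classification itself.

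**The true ICCs are assumed.** They are, and the false-group simulations give all sites a common value. The width of the sampling distribution is a per-site result, however, and does not depend on sites being alike.

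**The work is exploratory and its limits are acknowledged.** It is exploratory, but the acknowledgement concerns power to find markers.

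**Conclusion.** The concern holds in a limited form. Four duplicates cannot support assigning individual CpG sites to reliability groups. At an assumed true ICC of 0.8, one site in five would show an estimate below 0.5 and about one in four would exceed 0.9. Even an optimal rule would misplace 16% to 32% of sites between the pairs of ICC levels examined. Groups found by an ordinary normal or beta mixture on the raw ICCs would not be evidence of real differences in reliability, because widely separated groups can arise when there are none.

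This rests on reading the replicates as four samples run twice, on normal errors and on assumed true ICCs; the alternative readings lead to the same conclusion. The consequence is an unreliable assay-quality classification within an exploratory methylation analysis. The Ki-67 endpoint and the planned site-by-site tests are untouched, since nothing in the plan passes the groups on to them.

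**What to change.** Amend Section 13.5 before the methylation data are analysed.

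1. State which tissue supplies the duplicates, how many samples are duplicated and how many runs each has.
2. Do not assign individual CpG sites to groups from raw ICCs. Either report the ICC distribution descriptively, or fit a mixture whose components carry the F(3,4) sampling error (or its equivalent for the design actually used), with a one-group check and posterior membership probabilities in place of fixed labels.
3. If per-site reliability is wanted, compute 1 - technical variance/total variance, with technical variance from the duplicates and total variance from all study arrays of the same tissue. As an illustration, take a true reliability of 0.8, 30 arrays (the planned number of evaluable patients) and the two variance estimates as independent. The estimate is then 1 - 0.2 × F(4,29), and it falls below 0.5 with probability P(F(4,29) > 2.5) = 0.064, against 0.197 from the four-pair ICC.
4. Shrink the technical variance across sites only if the data support a common prior. In simulation, shrinkage cut misclassification at a 0.5 cut-off from 28% to 17% when technical variance was fairly homogeneous across sites, but raised it from 29% to 33% when it was not.

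The cost is revised SAP wording and a little more analysis, with no new arrays or participants. The price is fewer definite site labels, or none, and reliability statements confined to the tissue that supplied the duplicates.
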